5.1 Product Characteristics

Table 1 Investigational Product Information

Parameter	Memantine Hydrochloride (Active)	Placebo
Dosage form	Film-coated tablet	Film-coated tablet
Strength	10 mg per tablet	Not applicable
Route of administration	Oral	Oral
Storage conditions	Sealed container, 10 – 30 ° C	Sealed container, 10 – 30 ° C
Shelf life	48 months	48 months
Manufacturer	Lundbeck A/S, (Denmark)	Qilu Pharmaceutical Co., Ltd., (China)

The placebo tablets are indistinguishable from the active tablets in appearance, weight, taste, packaging, and dosing schedule but contain no memantine hydrochloride.

5.2 Dosing Regimen

Beginning on Day 1, participants in both the memantine and placebo groups will receive one-half tablet (5 mg) twice daily for 7 days. From Week 2 onward, the dose will be increased to one tablet (10 mg) twice daily and continued through the end of Week 6. The complete dosing schedule is summarized in Table 1.

Participants assigned to either memantine or matching placebo will follow a two-step, twice-daily schedule:

Table 2 Dosing Regimen

Study Week	Dose per administration	Total daily dose	Administration details*
Week 1	½ tablet (5 mg)	10 mg	Orally, at consistent morning and evening times (recommended interval, 12 h ± 2 h)
Weeks 2 – 6	1 tablet (10 mg)	20 mg	Orally, at consistent morning and evening times (recommended interval, 12 h ± 2 h)

* Each active tablet contains 10 mg memantine. Placebo tablets are identical in appearance, weight, packaging, and schedule but contain no active ingredient. The planned treatment duration is 42 – 45 days.

Dose Modification

The investigator may reduce the dose, interrupt treatment, or permanently discontinue the investigational product under the circumstances outlined below.

Dose Reduction — If a *moderate* AE occurs during the treatment phase and the investigator has ruled out causes unrelated to the study drug, the dose may be reduced from 1 tablet twice daily (BID) to $\frac{1}{2}$ tablet BID for 3 to 7 days. Should the AE lessen or resolve, the investigator may reinstate the full dose of 1 tablet BID.

Temporary Interruption — If a *moderate* AE occurs during the run-in period and substantially interferes with daily activities or work, and the investigator has ruled out non-drug-related causes, study treatment may be withheld for 3 to 7 days. Should the AE diminish or resolve, the participant may, at the investigator's discretion, re-enter the run-in phase and resume dosing as specified in the protocol.

Permanent Discontinuation — If a severe AE or SAE occurs after randomization, the investigator must instruct the participant to stop all study medication immediately and retrieve any unused investigational product and its packaging. The participant is to receive appropriate medical care, and the event must be documented in detail in the electronic case-report form.

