4.3.2 Investigator-Initiated Withdrawal

4.3.2.1 Discontinuation of Study Drug

The investigator may discontinue study treatment for safety or other compelling reasons, including:

- (1) Medical or ethical considerations that, in the investigator's judgement, necessitate cessation of treatment.
- (2) Allergic reactions, neuropsychiatric symptoms, or any other SAE requiring discontinuation.
- (3) An emergent clinical condition mandating alternative therapy.
- (4) Any unforeseen circumstance that, in the investigator's judgement, warrants early termination of treatment.

Participants who discontinue study drug for any of the above reasons must complete the early-termination visit and continue follow-up as outlined in the protocol (on-site or by telephone).

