8.2.4 Measures taken with Regard to Study Treatment

Any actions taken regarding the study treatment following an AE should be recorded according to the following classification criteria:

No Change

Dose Reduction: In the event of a moderate AE during the treatment phase, and after the investigator has excluded causes unrelated to the investigational product, the dose may be reduced from 1 tablet twice daily (bid) to $\frac{1}{2}$ tablet bid for 3 – 7 days. If the AE improves or resolves, the investigator may reassess and restore the full dose of 1 tablet bid.

Treatment Interruption: If a moderate AE occurs during the run-in phase and significantly affects daily activities or work, and after the investigator has ruled out causes unrelated to the investigational product, treatment may be interrupted for 3 – 7 days. If the AE improves or resolves, the investigator may reassess and allow the participant to re-enter the run-in phase.

Permanent Discontinuation: If a severe adverse event (AE) or SAE occurs after randomization, the investigator must instruct the participant to discontinue the investigational product immediately. The investigational product packaging and any remaining medication must be returned, and appropriate clinical care should be provided.

Not Applicable

Unknown

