8.4 Observation and Management of Special Adverse Events

(1) In clinical trials, investigators must closely monitor participants for any AEs or SAEs that occur following the administration of the investigational product, to ensure prompt identification and management.

(2) For participants experiencing common adverse reactions associated with the investigational product, the investigator must immediately report the event to the Principal Investigator (PI). Based on the severity of the event, the investigator will determine the necessary diagnostic and therapeutic measures, and decide whether discontinuation of the trial is required. All AEs must be followed up, with detailed records of the actions taken and outcomes. Follow-up should continue until the event is resolved or the participant's condition stabilizes. If laboratory abnormalities occur, monitoring should continue until the values return to normal. The method of follow-up (e.g., inpatient, outpatient, home visit, telephone, or written communication) should be chosen based on the severity of the AE.

(3) For serious adverse events, the investigator should immediately provide emergency treatment according to standard operating procedures (SOP) and document the actions taken. A consultation with the relevant medical specialists should be requested. In urgent situations, the participant should be transferred to the ICU with medical staff accompaniment. The PI at the study site must be notified immediately, and the sponsor should be informed without delay.

(4) After any serious adverse event in a clinical trial, the investigator is required to report the SAE to the sponsor and the ethics committee immediately, and no later than 24 hours after becoming aware of the event. Relevant reports and information will be compiled in the investigator's file and updated as necessary.

In the case of death, the investigator must provide the sponsor and the ethics committee with all necessary documentation, such as the autopsy report and final medical report. The investigator must continue to follow up on all SAEs. Any new information obtained after the initial report should be submitted in a follow-up SAE report, which should be submitted in the same format and within the same timeframe as the initial report.

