If a participant develops new symptoms or signs of heart failure, or if pre-existing symptoms worsen, and they meet the criteria outlined in the table below, the investigator must promptly document these symptoms and assess the possibility of new or worsening heart failure. NT-pro BNP (preferably) or BNP levels should be measured, and chest X-ray or lung ultrasound and echocardiography should be performed. If NT-pro BNP ≥ 300 ng/L or BNP ≥ 100 ng/L, with X-ray or lung ultrasound indicating pulmonary congestion, and echocardiography showing cardiac structural or functional abnormalities, the event should be classified as new or worsening heart failure. The

cause of heart failure should be investigated: if related to the underlying disease, continue treatment; if related to memantine, for mild heart failure, discontinue the medication and prescribe anti-heart failure medications in an outpatient setting; for moderate to severe heart failure, hospitalization is required.

Table 6 Clinical manifestations of acute heart failure

Left Heart Failure Symptoms	Left Heart Failure Signs
exertional dyspnea	Wet rales in the lungs
Nocturnal paroxysmal dyspnea	Widened apical beat range
Resting dyspnea or sit-up breathing	Pathologic 3rd heart sound (gallop rhythm)
Coughing at night or lying down	
Decreased exercise tolerance	
Right Heart Failure Symptoms	Right Heart Failure Signs
Loss of appetite (poor appetite), abdominal bloating, nausea	Elevated jugular venous pressure (engorged or raging external jugular veins)
	Positive hepatic jugular venous reflux sign
	Peripheral edema (lower extremities or low hanging body parts)
	Pleural effusion, abdominal effusion and other plasma cavities

4) Bradycardia:

If a participant's daytime or ambulatory ECG shows an average heart rate of <50 bpm, or even <40 bpm, with or without symptoms such as dizziness, fatigue, weakness, poor concentration, syncope, chest tightness, palpitations, or shortness of breath, the following management steps should be taken:

If the heart rate is <50 bpm, discontinue the study drug and monitor.

If the heart rate is 40–50 bpm and associated with symptoms, hospitalization and management are required.

If asymptomatic, discontinue the drug and closely monitor, with daily reporting of heart rate and symptoms.

If the heart rate is <40 bpm, hospitalization is required for further management.

9. Ethical Principles and Requirements for Clinical Research

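### Protocol 5.2 and 8.2.4 require study drug to stop after any severe AE or SAE whatever the cause, but the heart-failure paragraph of 8.4 makes stopping depend on cause; the sections need reconciling.

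*Protocol*

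**What the plan says.** Four places in the protocol govern study drug after a serious or severe event.

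- **Section 5.2, Permanent Discontinuation:** "If a severe AE or SAE occurs after randomization, the investigator must instruct the participant to stop all study medication immediately". The sentence that introduces all the dose-modification rules in that section is permissive: "The investigator may reduce the dose, interrupt treatment, or permanently discontinue the investigational product under the circumstances outlined below".
- **Section 8.2.4:** "If a severe adverse event (AE) or SAE occurs after randomization, the investigator must instruct the participant to discontinue the investigational product immediately". This is the 5.2 rule again, in nearly the same terms.
- **Section 4.3.2.1:** "The investigator may discontinue study treatment for safety or other compelling reasons, including", followed by a list. One item reads "Allergic reactions, neuropsychiatric symptoms, or any other SAE requiring discontinuation".
- **Section 8.4, item (6) 3), New or Worsening Heart Failure:** once the event is classified, its cause is to be investigated, and then "if related to the underlying disease, continue treatment; if related to memantine, for mild heart failure, discontinue the medication".

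Section 8.1.2 makes an event serious if it leads to inpatient admission or a longer stay. The exceptions listed there include stays under 12 hours and admissions planned before the first dose.

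**The concern.** Sections 5.2 and 8.2.4 decide on severity or seriousness alone. The heart-failure paragraph of 8.4 decides on attributed cause. An event can be serious and also attributed to the underlying disease, so the two tests can point in opposite directions for the same participant.

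Heart failure is a foreseen event: new-onset heart failure is named among the safety endpoints in Protocol 2.2.2. About 20 hospitals are planned (Protocol 3.2), and each could follow a different section in good faith.

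The first thing at stake is participant safety, because the instruction on whether dosing goes on after a serious event is not unique. The second is consistent classification:

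- Continued dosing after an SAE breaches 5.2 but may comply with 8.4. Whether it counts as a major deviation, and so whether the participant stays in the per-protocol set (Protocol 7.2, SAP 2.2), depends on the section applied.
- The SAP tabulates TEAEs leading to permanent discontinuation (4.3.2.1 and 4.3.2.2). That count depends on which rule each site followed.

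**Working it through.** No arithmetic applies. The check sets the rules side by side and takes one event through them.

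| Place | Trigger | Depends on cause? | Instruction on study drug |
|---|---|---|---|
| 5.2, permanent discontinuation | Severe AE or SAE after randomization | No | Must stop |
| 8.2.4 | Same | No | Must stop |
| 5.2, opening sentence | Circumstances listed in 5.2 | Not stated | May stop |
| 4.3.2.1 | Safety or other compelling reasons | Not stated | May stop |
| 8.4 (6) 3), underlying disease | Classified heart failure | Yes | Continue, if *treatment* means study drug |
| 8.4 (6) 3), memantine, mild | Classified heart failure | Yes | Stop |

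**Test event.** A participant is admitted with worsening heart failure, and the investigator attributes it to the underlying disease.

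1. Under 8.1.2 the admission makes the event an SAE, unless a listed exception applies.
2. Under 5.2 and 8.2.4 study drug must stop. Attribution plays no part.
3. Under 8.4 the instruction is "if related to the underlying disease, continue treatment".
4. Steps 2 and 3 are incompatible if *treatment* means study drug.

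**What *treatment* means.** Two features of the sentence favour study drug. The instruction is set against stopping the medication if memantine is the cause, and heart-failure therapy is named separately in the second branch. Against this, continuing treatment could mean continuing to treat the underlying disease. The sentence does not decide the matter.

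**When the conflict arises.** Three conditions must hold together: (a) the event is severe or serious; (b) it is attributed to the underlying disease; (c) *treatment* means study drug. The diagnostic criteria in 8.4 (symptoms or signs, natriuretic peptide, imaging, echocardiography) can also be met by a non-serious, non-severe outpatient event. The mandatory rule in 5.2 does not reach that event, so nothing conflicts.

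**The rest of 8.4 (6).** The bradycardia paragraph calls for stopping. The seizure paragraph places its stopping steps after a judgement of relatedness and is silent on unrelated seizures. The psychiatric paragraph requires admission for moderate to severe symptoms without mentioning study drug. Silence is not contradiction, so these are not counted.

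**Is there a tie-break?** Protocol 7.3.2 gives the SAP precedence over the protocol's overview of the analyses, but the SAP contains no stopping rule. No provision in the documents ranks these protocol sections against one another.

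**The case against.** The strongest reply has three parts.

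**A general permission can stand beside a specific duty.** Section 4.3.2.1 is an open list of reasons for which the investigator may stop drug, and its SAE item can be read as pointing to the SAEs for which 5.2 already requires stopping. This largely stands. A reader might infer that 4.3.2.1 flatly contradicts 5.2, but the wording supports only a weaker statement: it suggests that not every SAE requires stopping. The permissive opening of 5.2 adds to the unclarity, but it too is secondary.

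**The heart-failure conflict is narrow.** It needs the three conditions above. Entry excludes NYHA class III or IV and ejection fraction of 40% or less (Protocol 4.2), and dosing lasts 42 to 45 days, so cases are plausibly few. This stands as a limit on size, but it does not remove the incompatibility when a case occurs.

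**The primary analysis is not compromised.** A reader might infer that values recorded after stopping are analysed as if the participant were still on drug. The documents do not say so. The full analysis set analyses participants as randomised (Protocol 7.2, SAP 2.2), and those who stop drug continue scheduled assessments (Protocol 4.3.2.1 and 4.4). Including their later recordings follows from that approach. Nor can a shift in the treatment difference be derived, because no event rate is given.

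A reader might also cite 8.4 (2), which has the investigator "decide whether discontinuation of the trial is required". That item concerns common adverse reactions and refers to stopping the trial. It is not a rule on study drug after a severe AE or SAE, so it does not support the point.

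**Conclusion.** The point holds in a limited form. Sections 5.2 and 8.2.4 impose an unconditional stop after any severe AE or SAE, while the heart-failure paragraph of 8.4 makes stopping conditional on cause. For a severe or serious heart-failure event attributed to the underlying disease, the instructions are incompatible if *treatment* means study drug. If it means other therapy, that direct conflict disappears, but the sentence still needs clarifying. The wording of 4.3.2.1 and the opening of 5.2 are secondary inconsistencies under either reading.

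The size cannot be stated as a number, because the documents give no rate of severe AEs, SAEs or heart failure. The consequences are for participant safety and for two classifications: the deviations that define the per-protocol set, which the SAP uses only for sensitivity analyses (4.2), and the TEAEs counted as leading to permanent discontinuation. The documents do not support a claim of bias in the primary estimate.

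**What to change.** Reconcile Protocol 4.3.2.1, 5.2 (including its opening sentence), 8.2.4 and the heart-failure paragraph of 8.4, so that one consistent rule governs study drug after a severe AE or SAE. State in 8.4 whether the instruction to continue refers to study drug or to other therapy. Which rule is adopted is a clinical decision for the sponsor and investigators; this review takes no view.

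The cost is a protocol clarification, submitted to the ethics committee as Protocol 9.2 requires for amendments, and a memo to sites. The effect on conduct may be limited: the revision history of SAP version 2.0 (17 July 2025) says that enrolment had nearly reached 256 when the interim analysis was due. The clarification can still serve the analysis. SAP 4.1.2 has the deviation listing finalised before database lock, so the blinded team can record before then how continued dosing after a severe AE or SAE is to be classified, and apply it identically at all sites.

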5.3 Supply, Packaging and Labeling of Investigational Product

Sufficient quantities of investigational product will be supplied to each study site for the full duration of the trial. All products will be packaged and labelled in compliance with applicable regulatory requirements.

The memantine and matching placebo will be packaged identically. Each outer carton will display the statement "**For Clinical Trial Use Only**" together with the product name, kit number, batch number, expiration date, storage conditions, and sponsor name. Cartons and labels will be identical except for the unique kit number assigned to each package.

5.4 Investigational Product Accountability

Designated pharmacy personnel at each study site are responsible for the receipt, storage, dispensing, and reconciliation of all investigational product (IP). Complete, contemporaneous documentation must be maintained throughout the trial.

Table 3 Study Drug Handling and Accountability

Process	Requirements
Receipt	Upon delivery, the site pharmacist (or authorized designee) verifies the shipment against the packing list, completes and signs the drug-receipt form, and documents the date of receipt.
Storage	IP must be stored in a locked, access-controlled cabinet under the temperature conditions specified on the label (10 – 30 °C). Storage and handling procedures must comply with all applicable regulations.
Dispensing	IP is dispensed according to each participant's randomization number and corresponding kit number, as assigned by the IRT system.
Reconciliation	For every kit, the following details must be entered promptly and indelibly in the drug-accountability log: date dispensed, quantity issued, kit number, participant randomization number, return of empty packaging, and quantity of unused tablets returned or destroyed.
Inspection	All IP accountability records are subject to review by study monitors, auditors, and regulatory inspectors. Any discrepancies must be documented, investigated, and resolved in accordance with the sponsor's standard operating procedures.

5.5 Return and Destruction of Investigational Product

At study close-out, all unused, partially used, and empty investigational-product containers—together with their original packaging—must be returned to the sponsor for authorized destruction. Each shipment shall be accompanied by a fully completed, dated, and signed Drug-Accountability/Return Form.

The outer shipping carton must be clearly labelled with the protocol number, study-site identifier, and the statement **“Clinical Trial Material – Return for Destruction.”**

5.6 Concomitant Medications

From the signing of informed consent until the final study visit, any pharmacotherapy given for comorbid conditions or to treat adverse events must be documented in full.

Required details include the medication name, indication, dose, dosing frequency, start and stop dates/times, and route of administration.

5.7 Prohibited Medications

The following medications are prohibited throughout the study period:

- (1) NMDA antagonists, including amantadine, ketamine, dextromethorphan, and others.
- (2) Levodopa, dopamine receptor agonists, anticholinergic agents, and barbiturates.
- (3) Class I, II, III, and IV antiarrhythmic drugs, as well as other herbal medicines and/or traditional Chinese medicines with antiarrhythmic properties (except in cases where participants are unable to tolerate these medications due to severe symptoms).
- (4) Antispasmodic agents, including dantrolene, baclofen, and others.
- (5) Other medications that, in the investigator's judgment, may interfere with the efficacy or safety assessments.

5.8 Management of Intolerable PAC-Related Symptoms

If a participant develops severe, intolerable symptoms attributable to frequent PACs, the investigator may initiate adjunct therapy with the cardio-selective β -adrenergic blocker bisoprolol fumarate (5-mg per tablet). Treatment should start at 2.5 mg once daily (qd) and may be titrated, on the basis of heart rate and symptom control, to a maximum of 10 mg qd. Except under these circumstances, the use of class I–IV antiarrhythmic agents or any herbal/traditional Chinese medicines with antiarrhythmic properties is prohibited during the trial.

6. Study Procedures and Visit Schedule

The trial is divided into three phases: a screening period (Visit 1, V1), a treatment period (Visits 2–4, V2–V4), and a follow-up visit (Visit 5, V5). Participants will attend all visits as outlined in the protocol. Any AE occurring during the study will be followed until the event resolves, stabilizes, or the participant is lost to follow-up.

An overview of scheduled activities is provided in the study-flow diagram, and detailed requirements for each assessment are listed in Table 2. For participant safety, the investigator may increase the frequency of scheduled assessments or add unscheduled

assessments not specified in the flow diagram whenever clinically warranted (e.g., in response to an AE).

6.1 Study Flow Diagram

	Screening period ¹ (≤14d)	treatment period			follow-up period	early withdrawal Visits ²	Symptom initiation additional visit
manipulate	V1	V2	V3	V4	V5		
		D7±2d	D28±3d	D42±3d	D56±3d	Day of exit +7d	
Signed informed consent							
Symptom assessment ³							
Inclusion/exclusion criteria							
Demographic information							
Basic information ⁴							
Prior and co-morbidities, smoking and drinking, history of allergies ⁵							
History of prior non-drug treatment, prior drug therapies ⁶							
Vital signs ⁷							
NYHA Cardiac Function Classification							

Cardiac ultrasound							
Hematology tests ⁸							
Urine PH							
Blood or urine HCG ⁹							
12-lead ECG							
3-day cardiac patch monitoring ¹⁰							
Randomization	 (D0)						
Issuance and collection of diary cards	 (Issuance only)					 (Collection)	
Return of experimental drugs						 (If applicable)	
Adjustment of medication							
AEs and co-medication							
SF-36 Health Questionnaire Scores							

Table 4 Study Flow Diagram

Notes:

1. The screening period examination of this study can accept the relevant examination results of our center or the local tertiary hospital within 1 month prior to the informed date (acceptable at the judgment of the investigator, otherwise the relevant examination is required).
2. If a subject withdraws from the study after completing the end - of - treatment visit (V4), for the relevant examinations related to early withdrawal (excluding the 3 - day ECG patch monitoring), if the time interval from the V4 visit is \leq 7 days or the investigator determines that repetition is unnecessary, these examinations do not need to be repeated. However, the reason for not conducting

the examinations should be described in the original case report. Pregnancy tests should be carried out as required. If a subject withdraws before V4, regardless of whether the V3 visit has been completed, all relevant procedures for early withdrawal must be performed.

3. Symptom assessment: the assessment includes the nature of the PACs symptoms, the frequency and duration of the episodes, and whether the nature of the symptoms has changed.

Nature of symptoms: Palpitations, a fluttering or pounding sensation in the heart, a sense of the heart skipping beats, fatigue, weakness, shortness of breath, discomfort in the chest or precordial area, dizziness, etc.

Frequency of episodes: daily, weekly, monthly, etc;

Duration: minutes, hours, sustained;

Symptom scores:

Score 0: No symptoms;

Score 1: Mild symptoms, occasional palpitations that do not affect daily life;

Score 2: Moderate symptoms, frequent palpitations, mildly interfering with daily life;

Score 3: Severe symptoms with persistent palpitations that significantly interfere with daily life;

4. Basic information including height, weight, waist circumference, education level, etc;

5. Past medical history: hemorrhagic/ischemic stroke, transient ischemic attack, myocardial infarction, history of epilepsy or seizures, and psychiatric disorders;

6. History of prior medications: medication use within 4 weeks prior to screening; history of non-drug therapy (including surgery): history of non- drug therapy within 6 months prior to screening; collection of a full history of prior cardiac-related surgery;

7. Vital signs include temperature, blood pressure, pulse, and respiration;

8. Including routine blood, liver function (alanine aminotransferase, glutamic aminotransferase, gamma glutamyl transpeptidase, total bilirubin, direct bilirubin, indirect bilirubin), thyroid function (fT3, fT4, TSH), renal function (creatinine, urea nitrogen or urea, glomerular filtration rate), electrolytes (blood sodium, potassium, magnesium, calcium), blood lipids (total cholesterol, triglyceride, HDL cholesterol, LDL cholesterol ester), fasting blood glucose, glycated hemoglobin, NT-pro BNP (preferred) or BNP.

9. Female subjects of childbearing age should undergo blood or urine HCG test to exclude pregnancy.

10. The duration of drug administration in this study was 42-45 days, and the start time of 3-day (72h) ECG recorder monitoring for V3~V5 visits was D25~D28 for V3, D39~D42 for V4, and D53~D56 for V5, respectively. ECG monitoring for the V4 visit should be started 3 days prior to the end of the drug administration, and the 3 consecutive days (72h) of ECG recorder monitoring should be performed at D39, if the administration of drug was ended at D42. recorder monitoring needs to be performed at D39. If 3 consecutive days (72h) of ECG monitoring is performed at D42, the drug must be administered until D45; other operations for V3~V5 visits are performed from the day of the 3-day ECG monitoring on to the day of the removal of the ECG recorder.

Table 5 Specific requirements for each inspection item

Inspection item	Requirements and observables
vital signs	Temperature, blood pressure, pulse, respiration.
12-lead ECG	Heart rate, P-R interval, QRS wave duration, Q-Tc interval (calculated by Bazett's formula), presence of AFL, presence of AF, presence of atrioventricular block
Blood or urine pregnancy	Blood/urine human chorionic gonadotropin, fertile women only. For infertile women, please note the reason, e.g. menopause \geq 1 year, hysterectomy, sterilization, etc.
Laboratory tests	
 ➤ Routine blood count: white blood cell count, neutrophil ratio and count, lymphocyte ratio and count, red blood cell count, hemoglobin amount, red blood cell pressure volume, platelet count ➤ Liver function: alanine aminotransferase, glutamine aminotransferase, gamma glutamyl transpeptidase, total bilirubin, direct bilirubin, indirect bilirubin. ➤ Thyroid function: fT3, fT4, TSH; ➤ Renal function: creatinine, urea nitrogen or urea, glomerular filtration rate; ➤ Electrolytes: blood sodium, blood potassium, blood magnesium, blood calcium ➤ Lipids: total cholesterol, triglycerides, HDL cholesterol, LDL cholesterol esters ➤ Fasting glucose, glycosylated hemoglobin, NT-pro BNP (preferred) or BNP ➤ Urine PH
Ambulatory electrocardiograph monitoring	
 ➤ 24-hour average number and load of PACs, 24-hour average number and load of bouts of NSAT, 24-hour average episodes count of NSAT, SAT, AF, AFL ➤ Monitoring start time and end time, monitoring duration
Cardiac ultrasound	
 ➤ Left atrial internal diameter (mm), septal thickness (mm), left ventricular end-systolic internal diameter (mm), left ventricular end-diastolic internal diameter (mm), left ventricular ejection fraction (LVEF %)

Inspection item	Requirements and observables
NYHA Cardiac Function Classification	➤ Class I, II, III, IV

